5.2 Subject Exclusion Criteria

Subjects presenting with any of the following must not be included into the study:

1. History of allergy to drug in the iminosugar class;
2. Treatment with any investigational products or therapies within 30 days (or 5 half-lives, whichever is greater) prior to the first day of dosing;
3. Currently has, or has a history of, disease or dysfunction of the pulmonary, cardiovascular, endocrine, hematologic, neurological, immune, GI, genitourinary, or other body system, that is likely to affect the safety of the subject;
4. Creatinine clearance < 90 mL/min (based on Cockcroft-Gault equation);
5. Proteinuria greater than or equal to 1+;
6. At screening, Grade 1 or higher abnormalities in supine vital signs to include deviations in temperature, resting heart rate, blood pressure, and respiratory rate (may be repeated once); at check-in (Day -1), Grade 2 or higher abnormalities in supine vital signs (see [Appendix II](#)). A second set of values were added to the toxicity table for subjects who present with asymptomatic bradycardia at baseline at time of screening (<60 bpm);
7. Abnormalities of physical exam suggestive of conditions that would pose an increased risk to the subject;
8. Abnormal ECGs; however, abnormal readings for the following benign conditions will be acceptable for the study: sinus bradycardia, sinus arrhythmia, early repolarization, nonspecific ST-T wave pattern or changes, right axis deviation (axis 100 degrees or less), first degree AV block (PR interval less than 210ms), nonspecific intraventricular

conduction delay (QRS less than 120ms), indeterminate axis, and short PR interval (where no delta wave).

If an abnormal ECG finding is previously recorded, medically insignificant, and attributed to other causes (i.e. body habitus), Principal Investigator (PI) may elect to enroll the subject.

9. At screening, laboratory values outside of the normal range; however, the following list of parameters (see below table) are not considered exclusionary if values fall outside of the normal range. At baseline/check-in (Day -1), values that are Grade 2 or higher based on the toxicity grading scale ([Appendix II](#)).

Low Chemistry Values	High Chemistry Values	Urinalysis	Hematology Values	Low Coagulation Values
Alkaline Phosphatase	Chloride	High or low specific gravity	Low-Basophils	PT
AST	CPK less than 400 (CO2)	High or Low pH	Low-Eosinophils	aPTT

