The Day -1 laboratory test results (serum chemistry/hematology/urinalysis) are considered as baseline. Laboratory reports will be available before dosing on Day 1 and must be promptly reviewed by the PI. Any subjects having one or more baseline laboratory test results meeting Grade 2 or higher criteria on the toxicity grading scale in [Appendix II](#) are ineligible for study participation.

Days 1 through 8 and follow ups on Day 10 (± 1) and Day 15 (± 1):

- Hematology, clinical chemistry, & coagulation: A subset of hematology (PLT count), serum chemistry (AST, ALT), and coagulation (INR, PT, aPTT) assessments will be collected prior to the first dose only on Day 1. Full clinical chemistry, hematology, coagulation, and urinalysis testing will be performed on Days 2 through 8 and follow ups on Day 10 (± 1) and Day 15 (± 1).

- Fecal Occult Blood Assessment: Fecal occult blood assessments will be performed on Days 1 through 8 and Day 15. If any fecal occult blood test is positive during the study period, subject(s) will be evaluated and a test will be performed on all subsequent stool specimens until negative. If fecal occult blood remains positive (excluding for hemorrhoids) for 3 consecutive samples, subjects will be referred for a GI evaluation and will be withdrawn from the study.
- Vomitus Occult Blood: Occult blood assessments will be done on all vomitus.

All laboratory assessments will be done by the clinical site's certified laboratory. Laboratory toxicity grading will be determined by use of the FDA Guidance for Industry: *Toxicity Grading Scale for Healthy Adult and Adolescent Volunteers Enrolled in Preventive Vaccine Clinical Trials September 2007* and the *Division of Microbiology and Infectious Diseases (DMID) Adult Toxicity Table November 2007*, as modified for this study and appropriate for the administration of UV-4B ([Appendix II](#)).

Table 5: Safety Laboratory Tests

Hematology	Chemistry	Coagulation	Urinalysis	Occult Blood
RBC count	Alkaline phosphatase	INR ^[b]	pH	Fecal
RBC distribution width	ALT ^[b]	PT ^[b]	Specific gravity	Vomitus
WBC count ^[c]	AST ^[b]	aPTT ^[b]	Glucose	
Basophils	Total bilirubin		Ketones	
Eosinophils	Indirect Bilirubin			
Lymphocytes	Gamma-glutamyltransferase		Leukocyte esterase	
Monocytes	Lactate dehydrogenase ^[a]		Nitrites	
Neutrophils	Blood urea nitrogen		Occult blood	
Hematocrit	Creatinine		Protein	
Hemoglobin	Uric acid		RBCs/hpf	
Mean corpuscular hemoglobin	Sodium		WBCs/hpf	

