9.4 Type and Duration of Follow-up of Subjects after Adverse Events

The collection of laboratory data will be limited to those parameters listed in [Section 8.2.1](#). Abnormal laboratory test values or abnormal clinical findings such as heart rate will be recorded using the FDA Guidance for Industry: *Toxicity Grading Scale for Healthy Adult and Adolescent Volunteers Enrolled in Preventive Vaccine Clinical Trials September 2007* (with the exception of sodium and potassium [see [Section 9.2.1](#)]). However, the grading is modified for sodium and potassium since there is significant overlap between laboratory normal values and Grade 1 and 2 toxicity criteria using this grading scale (Section 9.2.1). The QT interval will be corrected using the Fridericia formula (QTcF). All AEs will be monitored until they are resolved or are clearly determined to be due to a subject's stable or chronic condition or intercurrent illness(es).

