9.6 Study Halting Criteria

General:

- Any SAE
- Three or more subjects within a cohort, with the same Grade 2 event ;
- Any single Grade 3 or above finding (with the exception of aPTT as explained below);
- Evidence of hematemesis or hematochezia in 2 or more subjects
- Any other findings that, at the discretion of the PI, indicate that the study should be halted;

Electrocardiograph (ECG):

Two or more subjects within a cohort who meet any of the criteria below:

- PR: >220 ms
- QRS: >120 ms
- QTcF > 450 ms for men and >470 ms for women; or
- Change from baseline (average of pre-dose triplicate ECGs): QTcF >60 ms.

Decisions are to be based on an average QTcF value of triplicate ECGs. If an ECG demonstrates a prolonged QT interval, 2 more ECGs should be obtained over a 10 minute period. The averaged QTcF values of the 3 ECGs will then be used for decision making.

Laboratory criteria:

- Two or more subjects within a cohort have a Grade 3 increase in aPTT (confirmed on repeat) as defined by the FDA toxicity grading scale as modified for this study and as appropriate for the administration of UV-4B ([Appendix II](#)).

If any of the above events occur, the study will be halted and the SMC will review the available safety data to determine if the study should proceed as planned. If none of the events described above have been observed, dose escalation will proceed according to the protocol requirements.

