9.7 Individual Dose Limiting Toxicity

- Any single grade 3 AE or Lab abnormality
- Fecal occult blood remains positive for 3 consecutive stool samples, hemorrhoids are excluded
- Evidence of frank hematemesis or hematochezia/melena of any duration
- Any clinical signs or symptoms the PI has determined is unsafe to administer IP

If an individual subject in a cohort reaches dose limit toxicity as determined by any of the above criteria, the subject will not receive any additional doses, and will be withdrawn from the study. All subjects withdrawn from the study will undergo routine follow up safety monitoring.

9.8 Safety Oversight (Safety Review Committee, Independent Safety Monitor plus Safety Monitoring Committee)

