Myalgia	No interference with activity	Some interference with activity	Significant; prevents daily activity	Emergency room visit or hospitalization

AE = adverse event; CRF = case report form
 
All graded values representing a change from baseline must be reported as AEs. For clinical or laboratory observations not addressed by the toxicity grading criteria, Grade 0 = absent will be used in the AE CRF to indicate the toxicity grading criteria do not apply.
				

Systemic (General)	Mild (Grade 1)	Moderate (Grade 2)	Severe (Grade 3)	Potentially Life Threatening (Grade 4)
Illness or clinical AE (as defined according to applicable regulations)	No interference with activity	Some interference with activity, not requiring medical intervention	Prevents daily activity and requires medical intervention	Emergency room visit or hospitalization

AE = adverse event; CRF = case report form
 
All graded values representing a change from baseline must be reported as AEs. For clinical or laboratory observations not addressed by the toxicity grading criteria, Grade 0 = absent will be used in the AE CRF to indicate the toxicity grading criteria do not apply.
				

Serum	Mild (Grade 1)	Moderate (Grade 2)	Severe (Grade 3)	Potentially Life Threatening (Grade 4)
Sodium – hyponatremia mEq/L	132 – 134	130 – 131	125 – 129	<125
Sodium – hypernatremia mEq/L	148 – 150	151 – 153	>154	Associated with seizures
Potassium – hyperkalemia mEq/L	5.3 – 5.4	5.5 – 5.6	>5.6	Associated with ECG changes
Potassium – hypokalemia mEq/L	3.0 – 3.5	2.5 – 2.9	2.0 – 2.4	≤1.9
Glucose – hypoglycemia mg/dL	65 – 69	55 – 64	45 – 54	<45
Glucose – hyperglycemia fasting mg/dL random mg/dL	100 – 110 111 – 125	111 – 125 126 – 200	>125 >200	Insulin requirements or hyperosmolar coma
Blood urea nitrogen increase mg/dL	21 – 26	27 – 31	>31	Requires dialysis
Creatinine increase mg/dL	1.5 – 1.7	1.8 – 2.0	2.1 – 2.5	>2.5 or requires dialysis
Calcium – hypocalcemia mg/dL	8.0 – 8.8	7.5 – 7.9	7.0 – 7.4	<7.0
Calcium – hypercalcemia mg/dL	10.6 – 11.0	11.1 – 11.5	11.6 – 12.0	>12.0
Magnesium – hypomagnesemia mg/dL	1.3 – 1.7	1.1 – 1.2	0.9 – 1.0	<0.9
Phosphorous – hypophosphatemia mg/dL	2.3 – 2.5	2.0 – 2.2	1.6 – 1.9	<1.6
Creatine phosphokinase – increase by factor	2.0 – 5.0 x ULN	5.1 – 10.0 x ULN	10.1 – 20 x ULN	>20 x ULN
Albumin – hypoalbuminemia g/dL	2.8 – 3.3	2.5 – 2.7	<2.5	--
Total protein – hypoproteinemia g/dL	5.5 – 5.9	5.0 – 5.4	<5.0	--

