Alkaline phosphate – increase by factor	2.0 – 2.9 x ULN	3.0 – 5.0 x ULN	>5.0 – 10.0 x ULN	>10.0 x ULN
Liver function tests – ALT, AST increase by factor	1.1 – 2.5 x ULN	2.6 – 5.0 x ULN	5.1 – 10 x ULN	>10 x ULN
Bilirubin – when accompanied by any increase in liver function test increase by factor	1.1 – 1.25 x ULN	1.26 – 1.5 x ULN	1.51 – 1.75 x ULN	>1.75 x ULN

Serum	Mild (Grade 1)	Moderate (Grade 2)	Severe (Grade 3)	Potentially Life Threatening (Grade 4)
Bilirubin – when liver function test is normal; increase by factor	1.1 – 1.5 x ULN	1.6 – 2.0 x ULN	2.1 – 3.0 x ULN	>3.0 x ULN
Cholesterol increase mg/dL	201 – 210	211 – 225	>226	--
Pancreatic enzymes – amylase, and lipase – increase by factor	1.5 – 2.0 x ULN	2.1 – 3.0 x ULN	3.1 – 5.0 x ULN	>5.0 x ULN
AE = adverse event; ALT = alanine aminotransferase; AST = aspartate aminotransferase; CRF = case report form; ECG = electrocardiogram; ULN = upper limit of normal Criteria are modified for this study based on reference values. All graded values representing a change from baseline must be reported as AEs. For clinical or laboratory observations not addressed by the toxicity grading criteria, Grade 0 = absent will be used in the AE CRF to indicate the toxicity grading criteria do not apply.				

Hematology	Mild (Grade 1)	Moderate (Grade 2)	Severe (Grade 3)	Potentially Life Threatening (Grade 4)
Hemoglobin (Female) decrease - gm/dL	10.5-11.5	9.5-10.4	8.0 – 9.4	< 8.0
Hemoglobin (Female) change from baseline value - gm/dL	Any decrease – 1.5	1.6 – 2.0	2.1 – 5.0	> 5.0
Hemoglobin (Male) decrease - gm/dL	12.5 – 13.5	10.5 – 12.4	8.5 – 10.4	< 8.5
Hemoglobin (Male) change from baseline value – gm/dL	Any decrease – 1.5	1.6 – 2.0	2.1 – 5.0	> 5.0
WBC increase - cell/mm ³	10,901 – 15,000	15,001 – 20,000	20,001 – 25,000	> 25,000
WBC decrease - cell/mm ³	2,500 – 3,500	1,500 – 2,499	1,000 – 1,499	< 1,000
Lymphocytes decrease - cell/mm ³	750 – 1,000	500 – 749	250 – 499	< 250
Neutrophils decrease – cell/mm ³	1500-2000	1000-1,499	500-999	< 500
Eosinophils increase - cell/mm ³	650 – 1500	1501 – 5000	> 5000	Hypereosinophilic
PLT decrease - /mm ³	75,000 – 99,000	50,000 – 74,999	20,000 – 49,999	<20,000
PT – increase by factor	1.0 – 1.10 x ULN	1.11 – 1.20 x ULN	1.21 – 1.25 x ULN	> 1.25 ULN
PTT – increase by factor (partial thromboplastin time)	1.0 – 1.2 x ULN	1.21 – 1.4 x ULN	1.41 – 1.5 x ULN	> 1.5 x ULN
Fibrinogen increase - mg/dL	400-500	501-600	>600	--

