10.7.4 Clinical Laboratory Parameters

Observed values and change from baseline data for clinical laboratory parameters (hematology, serum chemistry, coagulation, urinalysis) will be summarized by treatment. Baseline is considered as the last laboratory test result collected before the first dose.

Shift tables will be presented for serum chemistry, hematology, coagulation, and urinalysis parameters according to laboratory toxicity grading. The grading of laboratory findings was based on the *FDA Guidance for Industry: Toxicity Grading Scale for Healthy Adult and Adolescent Volunteers Enrolled in Preventive Vaccine Clinical Trials September 2007* and *Division of Microbiology and Infectious Diseases (DMID) Adult Toxicity Table November 2007* as modified for this study (found in Appendix II of the protocol). A summary of clinical laboratory values of toxicity Grade 1 or higher will also be provided by parameter and treatment.

Individual subject data listings (serum chemistry, hematology, coagulation, and urinalysis) will be provided to summarize all laboratory values including change from baseline, all laboratory values outside the clinical reference ranges, and all laboratory values of toxicity Grade 1 or higher.

Values for any serum chemistry, hematology, coagulation, and urinalysis values outside the clinical reference ranges and also meeting toxicity grading criteria will be flagged on the individual subject data listings.

Fecal and vomitus occult blood findings will be summarized and listed by treatment and study day.

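### A serum sodium of exactly 154 mEq/L has no toxicity grade, so the graded entry, halting and stopping rules pass over it

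*Protocol*

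**What the plan says.** Protocol Appendix II, Serum, grades high sodium as "Sodium – hypernatremia mEq/L 148 – 150 151 – 153 >154" for Grades 1 to 3. Grade 4 has no numeric limit and applies only when there are seizures. The footnote to the table adds: "For clinical or laboratory observations not addressed by the toxicity grading criteria, Grade 0 = absent will be used in the AE CRF".

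Section 9.4 treats sodium as an exception to the FDA vaccine-trial scale: "the grading is modified for sodium and potassium since there is significant overlap between laboratory normal values and Grade 1 and 2 toxicity criteria".

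The grades then feed several rules:

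- Entry, Protocol 5.2, exclusion criterion 9: "At baseline/check-in (Day -1), values that are Grade 2 or higher based on the toxicity grading scale". Section 8.2.1 repeats it: "Any subjects having one or more baseline laboratory test results meeting Grade 2 or higher criteria" are ineligible.
- Study halting, Protocol 9.6: "Any single Grade 3 or above finding", with an exception for aPTT only. Three subjects in a cohort with the same Grade 2 event also halt the study.
- Individual stopping, Protocol 9.7: "Any single grade 3 AE or Lab abnormality".
- Reporting, SAP 10.7.4: "A summary of clinical laboratory values of toxicity Grade 1 or higher will also be provided by parameter and treatment". SAP 11 gives the Safety Monitoring Committee (SMC) the same Grade 1-or-higher incidences after each cohort.

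**The concern.** The Grade 2 and Grade 3 cells do not meet. The value between them, 154, is higher than values that exclude a subject and one unit below a value that halts the study, yet it has no grade of its own. Graded rules should become stricter as the value rises. Here they tighten, lapse for one value and then tighten again. A site that met this value would have to decide what the table meant, and the protocol allows two sites, so two investigators could decide differently. The stake is the consistency of a prespecified safety threshold.

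**Working it through.** **Inputs.** The hypernatremia cells in Appendix II; the graded rules in Protocol 5.2, 8.2.1, 9.6 and 9.7; the laboratory schedule in Protocol 8.2.1 and Appendix IV. Sodium is taken as reported in whole mEq/L, as the cells are written, and seizures are taken as absent.

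**Step 1: grade each value as printed, then apply the rules.**

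| Sodium (mEq/L) | Grade | Day -1 exclusion (Grade ≥2) | Counts toward three-subject Grade 2 halt | Single Grade ≥3 halt | Individual Grade 3 stop |
|---|---|---|---|---|---|
| 148 to 150 | 1 | no | no | no | no |
| 151 to 153 | 2 | yes | yes | no | no |
| 154 | none | no | no | no | no |
| 155 and above | 3 | yes | not applicable | yes | yes |

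From 148 upward, 154 is the only whole number without a grade.

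**Step 2: is this the table's usual way of writing a boundary?** Among the serum and hematology analytes in Table 5 of the protocol, six rows have an open-ended Grade 3:

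| Row | Grade 2 limit | Grade 3 |
|---|---|---|
| Potassium, high | 5.6 | >5.6 |
| Blood urea nitrogen | 31 | >31 |
| Albumin | 2.5 | <2.5 |
| Total protein | 5.0 | <5.0 |
| Eosinophils | 5000 | >5000 |
| Sodium, high | 153 | >154 |

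Five of the six repeat the Grade 2 limit as the Grade 3 bound; sodium does not. A ≥ sign lost in text extraction is unlikely, because a ≤ sign survives in the hypokalemia row of the same table (≤1.9).

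**Step 3: does other text supply a grade?** Section 9.4 takes sodium off the FDA scale. Sections 8.2.1, 9.2.1 and 9.2.3 name two source scales, FDA and DMID, but as modified for this study in Appendix II, so Appendix II is the operative scale. The footnote points to Grade 0 for anything the criteria do not address.

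**Step 4: number of results exposed.** The full chemistry panel is run on Days 2 to 8 (7 results) and on Days 10 and 15 (2 results): 7 + 2 = 9 per subject.

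- Per cohort of 8: 9 × 8 = 72.
- Three cohorts with set doses: 72 × 3 = 216.
- Five cohorts, if 4 and 5 are added by amendment: 72 × 5 = 360.

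These counts include placebo subjects. They are denominators only.

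**Step 5: repeat Step 1 with Grade 3 written as ≥154.** A value of 154 becomes Grade 3 and meets the Day -1 exclusion, the single-finding halt and the individual stop. No other whole-number value changes grade.

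**The case against.** The strongest reply is that nobody would record 154 as Grade 0. Hypernatremia has its own row, so it is arguably addressed by the criteria, and a sensible reader would see a boundary slip and assign Grade 2 or 3. That is fair as a prediction, and the Grade 0 step is an inference from the footnote. But the reader would still have to choose between Grade 2 and Grade 3, and that choice decides whether the study halts.

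A symptomatic subject could also be graded through the general row for illness or clinical AEs. This stands, and it means the gap matters mainly for a laboratory finding without symptoms. That row does not grade the sodium value itself.

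The ungraded safeguards are substantial:

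- Out-of-range sodium excludes at screening, because sodium is not in the exception table (5.2).
- Deterioration from baseline is an AE (9.2.3), and the investigator rates severity separately from grade (9.2.1).
- Laboratory reports return the same day with out-of-range values flagged (9.1.6).
- The investigator may exclude a subject (5.2), halt the study (9.6) or stop dosing for clinical signs or symptoms (9.7).
- The SMC and FDA review every cohort (9.5), and all values are listed (SAP 10.7.4).

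These make harm unlikely and keep the point minor. They do so by discretion, without giving 154 a grade.

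Cholesterol has the same slip (Grade 2 ends at 225, Grade 3 is >226), so sodium is not unique in the appendix. Cholesterol is not in the Table 5 panel, so that gap has no planned measurement behind it.

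**Conclusion.** The concern holds. Sodium of exactly 154 mEq/L without seizures has no grade under Appendix II as printed. Read literally, it meets none of the graded laboratory rules for entry, halting or stopping, and it is left out of the Grade 1-or-higher summaries. The documents show that the two cells do not meet; they do not show which one is wrong.

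The size is very small: one value of one analyte. No rate for it is given, and it should be rare in healthy subjects. The entry gap also needs an in-range sodium at screening followed by exactly 154 on Day -1, assuming the laboratory's upper limit lies below 154, which the documents do not state. This is a minor correction, worth making because the threshold drives decisions and costs almost nothing to repair.

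**What to change.** In Appendix II, change hypernatremia Grade 3 from >154 to ≥154 (the same as >153 for whole-number results). This is the more cautious choice: a single 154 would then meet 9.6 and 9.7. It also continues the two preceding bands of three units each (150 − 148 + 1 = 3 and 153 − 151 + 1 = 3). Band width is weak evidence of intent, since the hyponatremia bands span 3, 2 and 5 units.

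The sponsor should confirm the choice, because extending Grade 2 to 151–154 would also close the gap. Under that option 154 would exclude on Day -1 and count toward the three-subject Grade 2 halt, but on its own it would not meet a graded halting bullet or the Grade 3 stopping rule.

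The cost is one table cell, which could go into the amendment foreseen for Cohorts 4 and 5 or sooner. The cholesterol boundary could be corrected in the same edit. Visits, samples and analyses stay as they are.

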The collection of laboratory data is listed in [Section 8.2.1](#). The normal reference ranges utilized in this study are shown in the current version of the Laboratory Protocol Reference Ranges published by Lab. The grading of abnormal clinical findings are based on the FDA Guidance for Industry: *Toxicity Grading Scale for Healthy Adult and Adolescent Volunteers Enrolled in Preventive Vaccine Clinical Trials September 2007* and *Division Of Microbiology And Infectious Diseases (DMID) Adult Toxicity Table November 2007* as modified for this study (see [Appendix II](#)).

Any medical condition or graded laboratory value (according to [Appendix II](#)) after ingestion of the first dose or deterioration from the baseline condition will be reported and followed as an AE or, as appropriate, SAE. Attempts will be made to follow the subject closely to determine the outcome and duration of an event. Additional assessments including the repeat of laboratory tests and ECGs will be performed in an effort to monitor the subject as appropriate. If an event is ongoing at the time of study termination, permission will be requested from the subject to continue follow-up until the site PI or designee deems the event to be resolved, chronic, or the subject's condition to be medically stable. Abnormal ECGs, at the discretion of the PI, will be reviewed by a cardiologist.

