APPENDIX I SUBJECT FLOWDOWN

APPENDIX II UV-4B TOXICITY GRADING CRITERIA FOR NORMAL HUMAN SUBJECTS

Vital Signs*	Mild (Grade 1)	Moderate (Grade 2)	Severe (Grade 3)	Potentially Life Threatening (Grade 4)
Fever (°C)** (°F)**	38.0 – 38.4 100.4 – 101.1	38.5 – 38.9 101.2 – 102.0	39.0 – 40 102.1 – 104	>40 >104
Tachycardia – (beats per minute)	101 – 115	116 – 130	>130	Emergency room visit or hospitalization for arrhythmia
Bradycardia – (beats per minute)	50-54 if baseline >60	45-49 if baseline >60	<45 if baseline >60	Emergency room visit or hospitalization for arrhythmia
	45-50 if baseline ≤ 60	40-44 if baseline ≤ 60	<40 if baseline ≤ 60	
Hypertension (systolic) – mmHg	141 – 150	151 – 155	>155	Emergency room visit or hospitalization for malignant hypertension
Hypertension (diastolic) – mmHg	91 – 95	96 – 100	>100	Emergency room visit or hospitalization for malignant hypertension
Hypotension (systolic) – mmHg	85 – 89	80 – 84	<80	Emergency room visit or hospitalization for hypotensive shock
Respiratory Rate – breaths per minute	17-20	21-25	>25	Intubation

AE = adverse event; CRF = case report form
 * Subject should be at rest for all vital sign measurements.
 **Oral temperature; no recent hot or cold beverages or smoking
 All graded values representing a change from baseline must be reported as AEs. For clinical or laboratory observations not addressed by the toxicity grading criteria, Grade 0 = absent will be used in the AE CRF to indicate the toxicity grading criteria do not apply.

Systemic (General)	Mild (Grade 1)	Moderate (Grade 2)	Severe (Grade 3)	Potentially Life Threatening (Grade 4)
Nausea/vomiting	No to mild interference with activity or 1 to 2 episodes/24 hours	Moderate interference with activity or >2 episodes/24 hours	Prevents daily activity, requires outpatient IV hydration	Emergency room visit or hospitalization for hypotensive shock
Diarrhea	2 - 4 loose stools or < 400 gm/24 hours	5-6 stools or 400 – 800 gm/24 hours	7 or more watery stools or > 800gms/24 hours or requires outpatient IV hydration	Emergency room visit or hospitalization
Headache	No interference with activity	Repeated use of non-narcotic pain reliever > 24 hours or some interference with activity	Significant; any use of narcotic pain reliever or prevents daily activity	Emergency room visit or hospitalization
Fatigue	No interference with activity	Some interference with activity	Significant; prevents daily activity	Emergency room visit or hospitalization

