Fibrinogen decrease - mg/dL	150 – 200	125 – 149	100 – 124	< 100 or associated with gross bleeding or disseminated intravascular coagulation

PLT = platelet; PT = prothrombin time; PTT = partial thromboplastin time; ULN = upper limit of normal; WBC = white blood cell count

Criteria are modified for this study based on reference values.

All graded values representing a change from baseline must be reported as AEs. For clinical or laboratory observations not addressed by the toxicity grading criteria, Grade 0= absent will be used in the AE CRF to indicate the toxicity grading criteria do not apply.

Urine	Mild (Grade 1)	Moderate (Grade 2)	Severe (Grade 3)	Potentially Life Threatening (Grade 4)
Protein	Trace	1+	2+	Hospitalization or dialysis
Glucose	Trace	1+	2+	Hospitalization for hyperglycemia
Blood (microscopic) – RBC per high power field (RBC/hpf)	1-10	11 – 50	> 50 and/or gross Blood	Hospitalization or packed red blood cells transfusion

AE = adverse event; CRF = case report form; hpf = high power field; RBC = red blood cell
Criteria are modified for this study based on reference values.
All graded values representing a change from baseline must be reported as AEs. For clinical or laboratory observations not addressed by the toxicity grading criteria, Grade 0 = absent will be used in the AE CRF to indicate the toxicity grading criteria do not apply.

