10.7.2 Adverse Events

A treatment-emergent adverse event (TEAE) is defined as an AE that occurs after administration of the first dose of study product or that is already present prior to the first dose of study product and becomes more severe postdose. In this study AEs will be evaluated from time of the first dose administration through the last follow-up visit. A medical condition that exists at the time of screening will be recorded as an AE only when it deteriorates at any time after the first study dose administration.

All AEs must be graded for severity and relationship to study product per Section 9.2.1 of the Protocol. AEs will be coded using the Medical Dictionary for Regulatory Activities (MedDRA[®]) AE coding system, version 19.0.

All TEAEs will be summarized for all subjects in the safety population by maximum severity, relationship to the study drug (as assessed by the Principal Investigator [PI]), and initial onset day. Serious TEAEs will be summarized by maximum severity, and relationship to the study drug. TEAEs leading to treatment discontinuation will also be summarized by maximum severity and relationship to the study drug. The frequency including the number of TEAEs, the number of subjects experiencing a TEAE, and the percentage of subjects experiencing a TEAE will also be summarized and displayed. TEAEs summaries will be presented by treatment, and by MedDRA (Version 19.0) system organ class and preferred term.

All AEs, severe AEs, serious AEs, deaths (if any), and events resulting in study discontinuation will be listed. Any individual dose-limiting toxicity (Protocol Section 9.7) will also be listed.

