10.7.5 Vital Signs

Routine vital signs data (systolic and diastolic blood pressure, pulse rate, respiratory rate, and oral temperature) and orthostatic vital signs data (blood pressure and pulse rate) will be listed and summarized by treatment, along with changes from baseline, where baseline is defined as the last value prior to the first dose on Day 1, including unscheduled values. Orthostatic change is the standing value minus the supine value taken prior to the standing value.

A summary of vital signs values of toxicity Grade 1 or higher will also be provided by parameter and treatment. The grading of vital signs was based on the *FDA Guidance for Industry: Toxicity Grading Scale for Healthy Adult and Adolescent Volunteers Enrolled in Preventive Vaccine Clinical Trials September 2007* as modified for this study (found in Appendix II of the protocol).

For routine vital signs data, values outside the clinical reference ranges will be flagged on the individual subject data listing, as will the vital sign values meeting toxicity Grade 1 or higher.

The reference ranges for routine vital signs are: supine systolic blood pressure (90-140 mmHg), supine diastolic blood pressure (50-90 mmHg), supine pulse rate (40-100 bpm), respiratory rate (10-24 breaths/minute) and oral temperature (35.5°C -37.8°C).

Orthostatic decreases of ≥ 20 mmHg for systolic blood pressure or ≥ 10 mmHg for diastolic blood pressure or an increase in heart rate of > 30 bpm are considered to be of potential clinical concern and will also be highlighted on the individual data listings. Repeat and unscheduled readings will be handled as defined in Section 10.1.1.

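### Because any fall in hemoglobin counts as a reportable AE, the overall any-TEAE percentage will sit near its ceiling in every arm, and the SAP plans no version without these events

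*Protocol*

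**What the plan says.** **Grading.** The hematology table in Protocol Appendix II has a change-from-baseline row for hemoglobin in each sex. The Grade 1 band is "Any decrease – 1.5" g/dL. There is no minimum size, and the value need not leave the normal range.

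**Reporting.** The footnote to the table says "All graded values representing a change from baseline must be reported as AEs". Protocol 9.2.3 says the same of graded laboratory values: those arising "after ingestion of the first dose or deterioration from the baseline condition will be reported and followed as an AE or, as appropriate, SAE". Neither place exempts changes judged clinically unimportant.

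**Baseline and schedule.** Protocol 8.2.1: "The Day -1 laboratory test results (serum chemistry/hematology/urinalysis) are considered as baseline". SAP 10.7.4: "Baseline is considered as the last laboratory test result collected before the first dose". The Day 1 pre-dose hematology sample is for platelets only, so the two agree for hemoglobin unless there is an unscheduled value. Full hematology follows on Days 2 to 8, 10 and 15.

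**Analysis.** SAP 10.7.2 treats every AE starting after the first dose as treatment-emergent and says that "the percentage of subjects experiencing a TEAE will also be summarized and displayed". It also plans summaries by system organ class, preferred term, maximum severity, relationship and onset day. SAP 11 sends TEAE tables to the SMC after each cohort. SAP 10.7.8 plans no safety inference.

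**Vital signs.** Protocol 9.1.2 makes vital signs of Grade 1 or above AEs. Appendix II puts a respiratory rate of 17–20 in Grade 1, while SAP 10.7.5 gives a listing reference range of "respiratory rate (10-24 breaths/minute").

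**The concern.** Occurrence of AEs is the first primary outcome, and with no inference planned, the descriptive percentages carry the comparison of dose groups with pooled placebo. When one measurement is the reference and nine later ones are compared with it, at least one will usually be lower with no drug effect at all. Under these rules that lower value is a TEAE. A headline percentage that is high for reasons unrelated to drug has little room to show a dose pattern.

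The same events spread into other summaries:

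- In the maximum-severity table, subjects with no clinical event would appear as mild.
- The hemoglobin preferred-term row would itself be near its ceiling.
- The related-TEAE percentage may be affected, because Protocol 9.2.1 requires an AE to be called related when no other cause is found.

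**Working it through.** **1. Count of values.** Screening 1 + Day -1 1 + Days 2–8 7 + Day 10 1 + Day 15 1 = 11. This reproduces the 11 hematology samples in Protocol Table 6. Nine are post-dose, so k = 9. The plan states no expected TEAE rate to reproduce.

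**2. Exact case.** If the baseline and the k post-dose values are exchangeable (no drug effect, no drift, no serial correlation, no ties), then

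P(at least one value below baseline) = 1 − P(baseline is the lowest of k + 1) = k/(k + 1) = 9/10 = 90%, whatever the SD.

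Protocol 7.3.1 also lists hematology after dosing on Day 1, although 8.2.1 and Appendix IV do not. If it were drawn, the figure would be 10/11 = 90.9%.

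**3. Sensitivity.** The documents give no within-subject SD, correlation or reporting precision, so these are assumptions. Simulation with 400,000 subjects per setting, values rounded to 0.1 g/dL, no drift; percentage of subjects with at least one value below baseline:

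| Day-to-day correlation | SD 0.2 g/dL | SD 0.3 | SD 0.4 | SD 0.5 |
|---|---|---|---|---|
| 0 | 85 | 87 | 88 | 88 |
| 0.5 | 82 | 84 | 85 | 86 |
| 0.8 | 77 | 80 | 81 | 82 |

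A pure random walk without ties gives 1 − C(18,9)/2^18 = 81.5%. The no-drift range is therefore about 77–90%, with 90% as its upper end.

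**4. Blood sampling.** Table 6 schedules 486.6 mL per subject but gives no effect on hemoglobin. An assumed gradual fall of 0.3 g/dL by Day 8 gives 91–98%, and 0.6 g/dL gives 96–99.9%.

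**5. Expected counts.** At backgrounds of 77% and 90%:

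- a dose group of 6: 6 × 0.77 = 4.6 and 6 × 0.90 = 5.4 subjects;
- pooled placebo of 10 (five cohorts): 7.7 and 9.0;
- a whole cohort of 8, as in a blinded SMC table: 6.2 and 7.2.

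**6. Effect on the overall percentage.** Let b be the background and p the rate of other TEAEs, taken as independent. The overall rate is 1 − (1 − b)(1 − p), so a difference in p is multiplied by (1 − b): 0.10 at b = 0.90 and 0.23 at b = 0.77. For illustration, assume p = 30% on placebo and 70% on drug, a gap of 40 points:

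- b = 0.90: 1 − 0.10 × 0.70 = 93% and 1 − 0.10 × 0.30 = 97%; gap 4 points.
- b = 0.77: 1 − 0.23 × 0.70 = 84% and 1 − 0.23 × 0.30 = 93%; gap 9 points.

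**The case against.** **Other tables still work.** Protocol 11.4.5 rests the safety evaluation on how often AEs occur, how intense they are and what kind they are, not on one crude percentage. Hemoglobin events have their own preferred term, so the rows for diarrhea, nausea or headache are untouched. Small falls would normally be rated mild, so the moderate and severe rows stay largely clean. The Grade 2+ and shift tables are also unaffected. This stands, and it limits the point to the summaries named above.

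**No rule uses the percentage.** There is no hypothesis and no powered comparison, and no numerical trigger in Protocol 9.6 or 9.7 counts Grade 1 events. Groups of six resolve little anyway: as an illustration only, Fisher's exact test with 6 against 10 subjects has power 0.32 for assumed rates of 60% and 20% without the background. This stands as a limit on severity. With a 90% background, though, those rates become 96% and 92% and the power falls to 0.0006, so what little resolution there is disappears.

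**Inclusive reporting looks deliberate.** Appendix III lists reduced hemoglobin for two related drugs, and the Amendment 2 rationale confirms the intent. This also stands, and it is a reason to change the presentation rather than the reporting rule.

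**Supplementary tables are already allowed.** SAP 4 permits additional analyses, and the table shells are a separate document. They may already contain such a split, but the SAP text does not call for it, and it is better fixed before unblinding.

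**Respiratory rate.** The 10–24 range only flags listings, and Grade 1 values are flagged separately. Grade 1 supine vital signs exclude at screening (Protocol 5.2). An abnormal reading may be repeated twice, and if it stays abnormal the least abnormal value is graded (9.1.2). So respiratory rate may add to the background, but by an amount the documents do not let one quantify.

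**Conclusion.** The point holds for the overall any-TEAE percentage, the hemoglobin preferred-term row, the mild row of the maximum-severity table (which takes in nearly everyone with nothing worse) and possibly the related-TEAE percentage. If the plan is followed exactly, about 77–90% of subjects in any arm would have a hemoglobin TEAE with no drug effect. The range assumes SD 0.2–0.5 g/dL, day-to-day correlation 0–0.8 and rounding to 0.1 g/dL, with the exact exchangeable case at the top. A fall from blood sampling would raise it.

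A reader might infer that the safety analysis as a whole cannot separate doses, or that nine in ten is a firm figure. The documents support neither. The clinical preferred-term rows, the moderate and severe rows and the graded laboratory tables can still show a dose pattern. The 90% ignores ties and serial correlation, although seven of the nine samples fall on consecutive days. The shrinkage of a 40-point gap to 4–9 points rests on assumed rates and independence. This is a cheap improvement to the summary of a primary outcome, not a flaw that undermines the trial.

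**What to change.** In SAP 10.7.2, and in the SMC interim TEAE tables of SAP 11, present the overall, maximum-severity and relatedness TEAE summaries twice: once with all TEAEs, and once without events reported solely because a laboratory or vital-sign value met a Grade 1 row of Appendix II. Identify those events with a pre-specified flag in the AE dataset. Keep the underlying values in the grade tables of SAP 10.7.4 and 10.7.5, so that nothing drops out of view. Grading thresholds and AE reporting rules stay with the sponsor and need no change for this.

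The cost is one flag and one additional set of tables.
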